#### Analysis of the collected prescriptions:

The variables will be analysed separately for GPs, rheumatologists and orthopaedists / orthopaedic surgeons according to the information provided, as detailed above in § 9.3: Variables.

Possible selection bias will be assessed by comparing the distributions of available characteristics (e.g. country, age, gender, type of practice and specialty) between respondent and non-respondent physicians.

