**Figure 1: Study scheme and main timelines**

#### 9.2.1 Inclusion criteria

The survey will be conducted among physicians meeting the following inclusion criteria:

- Physicians who prescribed systemic thiocolchicoside within the 12 months prior to the survey
- GPs and specialists of any of those targeted for the DHPC and EM:
  - Rheumatologists
  - Orthopedists / orthopedic surgeons

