## 9.5 STUDY SIZE

### 9.5.1 Sampling plan

The statistical unit considered is the physician who prescribes systemic thiocolchicoside. For each selected country, the sample survey will include physicians identified and recruited from one source: IMS OneKey reference lists of required specialists.

These lists may not cover all of the physicians who received the DHPC and EM or may include physicians who were not targeted for the DHPC and EM. Consequently a screening question will check whether the physician has prescribed systemic thiocolchicoside within the last 12 months and therefore can be considered as a prescriber. These lists will be restricted to the targeted specialists' population, i.e. selected specialists who are currently active and not retired in 2016 at the time of the survey.

As per sample size defined below and the number of selected countries and specialties, physicians will be stratified only per country and specialty (Table 9.5.1–1). Other criteria such

as region, age and gender of the prescriber are less relevant than country and specialty, since they may not be available in all countries or not be a determinant as important as country or specialty. The use of more strata would have needed a larger sample size.

A random stratified sampling method will be applied. As a first step, all lists will be merged, and then the eligible physicians will be divided into homogeneous groups, called strata, which are mutually exclusive (a physician can only belong to one stratum). This stratification will be based on the following criteria:

- Country: 4 possibilities,
- Specialty: 3 possibilities.

Thus,  $4 \times 3 = 12$  strata will be formed.

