**Table 9.5.2–1: Sample size obtained for various precisions and proportions**

Margin of error for 95% CI				
Proportion	5%	4%	3%	2%
10%	139	216	384	864

30%	323	504	896	2,017
50%	384	600	1,067	2,401
70%	323	504	896	2,017
90%	139	216	384	864

Since the proportion of physicians informed about the updated prescribing conditions and recommendations for safe use of systemic thiocolchicoside is not known and there is no evidence supporting the expected proportion, the worst case hypothesis will be assumed considering that 50% of physicians will have received and understood the safety information distributed recently. This assumption yields the largest sample size.

Considering this hypothesis and in order to achieve a CI of 95% with a half-width of 4%, a total of 600 analysable physician questionnaires will be needed for the overall sample. Considering a margin of error of 5% (or 3% respectively) instead of 4%, the required sample size would be 384 (or 1,067) analysable physician questionnaires for the overall sample.

Based on IMS Medical Radar experience from previous similar surveys and estimates and the evaluation of the survey feasibility with four countries, the sample size of 600 is considered for this study. Indeed, the elected sample size should be sufficient to be divided between 4 countries and further between 3 groups of specialities.

It is estimated that about 30% of physicians will not complete the questionnaire until the end or not be analysable (i.e. physicians who respond to questions regarding their knowledge on the updated safety concerns of systemic thiocolchicoside or physicians without any prescription of systemic thiocolchicoside in the last 12 months or physicians who have to interrupt the interview due to an emergency (rare)). Taking into account these respondent physicians without analysable questionnaires, the overall sample size of 780 participating physicians will be required to reach 600 analysable questionnaires (i.e. recruitment of physicians should continue until 600 analysable questionnaires have been reached).

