**Table 9.5.2–4: Sample size per country and per specialty**

n (vertical % per country)*	France	Greece	Italy	Portugal	All
Number of physicians with an analysable questionnaire	180	120	180	120	600
GPs	90 (50.0%)	60 (50%)	90 (50.0%)	60 (50%)	300 (50%)
Rheumatologists	40 (22.2%)	30 (25%)	40 (22.2%)	30 (25%)	140 (23.3%)
Orthopedists / orthopaedic surgeons	50 (27.8%)	30 (25%)	50 (27.8%)	30 (25%)	160 (26.7%)
Number of participating physicians required	234	156	234	156	780
GPs	117 (50%)	78 (50%)	117 (50%)	78 (50%)	390 (50%)
Rheumatologists	52 (22.2%)	39 (25%)	52 (22.2%)	39 (25%)	182 (23.3%)
Orthopedists / orthopaedic surgeons	65 (27.8%)	39 (25%)	65 (27.8%)	39 (25%)	208 (26.7%)

\* To be aligned with the n by country, numbers n per specialty have been rounded to the most closed integer.

Since the relative weight of each country and of each specialty in the sampling plan is different from its real relative weight in estimations, the extrapolation of the raw survey results to the overall target population would not be relevant.

A sample adjustment will be performed. The survey results will be weighted to reflect the real proportion of the four countries and within each country to reflect the real proportion of each specialty in order to extend the survey results to the overall target population. Both unweighted (i.e. raw data) and weighted results will be presented in the report.

A weight variable will be applied to each statistical unit (i.e. the analysable physician) during the results calculation in order to correct any over-or under-sampling that may have occurred for a country or specialty. This weight variable will indicate how many unit(s) of the population of interest an observation will count in a statistical procedure. Its value will change per country and per specialty. The weights will be normalised to obtain their sum equal to the sample size.

In order to fill-in each stratum of the sample survey from the IMS OneKey reference files, an independent sample will be selected per stratum through a simple random sampling without replacement.

In each specific stratum, physicians will be contacted according to the order of draw in this stratum. If a physician does not want to participate in the survey, the next one in order of

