### 9.9.2 Possible selection bias due to voluntary participation

The potential for selection bias of physicians participating in a survey is an inherent bias/limitation to any study based on volunteer participation. In order to quantify any selection bias, the distribution of each stratification criterion of physicians (country and specialty) will be compared between participants and non-participants.

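### The planned selection-bias check compares country and specialty, which quota recruitment fixes among respondents, so it measures contact yield per stratum and not response bias within strata

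*Protocol*

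**What the plan says.** The protocol describes the check in three places.

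- Section 9.7.1, under the analysis of collected prescriptions: possible selection bias is to be "assessed by comparing the distributions of available characteristics (e.g. country, age, gender, type of practice and specialty) between respondent and non-respondent physicians".
- Section 9.9.2, with the stated purpose of quantifying selection bias: "the distribution of each stratification criterion of physicians (country and specialty) will be compared between participants and non-participants".
- Section 4.9 has a similar sentence, listing region where 9.7.1 lists country.

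Four other parts of the design bear on it.

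- **Sampling and quotas.** In section 9.5.2, "an independent sample will be selected per stratum through a simple random sampling without replacement". Table 9.5.2–4 sets the number of analysable questionnaires for each of the 12 strata, and section 9.6.1 stops recruitment in a stratum once its target is met.
- **Weighting.** Sections 9.5.2 and 9.7.1 weight results to the real mix of countries and of specialties.
- **Eligibility.** The first inclusion criterion in section 9.2.1 is "Physicians who prescribed systemic thiocolchicoside within the 12 months prior to the survey". The lists do not hold this information. Section 9.5.1 states: "Consequently a screening question will check whether the physician has prescribed systemic thiocolchicoside within the last 12 months".
- **Use of the word respondent.** Section 9.5.2 counts "physicians without any prescription of systemic thiocolchicoside in the last 12 months" among those whose questionnaires are not analysable, then continues: "Taking into account these respondent physicians without analysable questionnaires". There, a respondent can be a non-prescriber. Section 9.7.1 does not define the term.

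**The concern.** Country and specialty do not vary inside a country-by-specialty stratum, so comparing them can only be done across strata. With quotas, the respondent mix on these two variables is set by design. Only the non-respondent mix is free to move, and it moves with the number of contacts each quota used up. A difference is then a statement about yield, although section 9.9.2 offers it as a measure of selection bias. An absence of difference gives no reassurance about who volunteered within a stratum.

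Age, gender and practice type could carry that information, because the weights do not use them. Their value depends on two things the protocol leaves open: whether they are compared within strata, and who counts as a respondent.

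What is at stake is the reading of the results. Section 9.5.2 makes generalisation of the prescription data depend on the physician sample being shown to be generalisable, and section 9.9.5 extends weighted results to the target population. A check that answers a different question can support neither claim, nor qualify it.

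**Working it through.** **The plan's own figures.** The protocol gives no number for this check. Its sample size reproduces: 0.5 × 0.5 × 1.96² / 0.04² ≈ 600. Section 9.5.2 expects about ten contacts per analysable questionnaire, so about 6,000 contacts.

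**Step 1: what the specialty comparison measures.** Summed over countries, Table 9.5.2–4 gives quotas q of 300 GPs, 140 rheumatologists and 160 orthopaedists. With yield r per contact, contacts are q/r and non-respondents are q(1/r − 1). The respondent mix is always 50.0 / 23.3 / 26.7%. Only r moves the non-respondent mix. The same algebra applies to country.

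**Step 2: what follows if gender is pooled.** Assumed male shares are 60% (GPs), 55% (rheumatologists) and 95% (orthopaedists), with response unrelated to sex inside every stratum. The protocol gives neither sex shares nor yields by specialty. Men among respondents: (300 × 0.60 + 140 × 0.55 + 160 × 0.95) / 600 = 409/600 = 68.2%.

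| Assumed yield GP / rheum. / orth. | Non-respondent mix | Men, respondents | Men, non-respondents | Gap (points) |
|---|---|---|---|---|
| 10 / 10 / 10% | 50.0 / 23.3 / 26.7% | 68.2% | 68.2% | 0 |
| 7 / 15 / 15% | 70.1 / 14.0 / 15.9% | 68.2% | 64.9% | 3.3 |
| 5 / 15 / 20% | 79.9 / 11.1 / 9.0% | 68.2% | 62.6% | 5.6 |
| 10 / 10 / 5% | 38.6 / 18.0 / 43.4% | 68.2% | 74.3% | 6.1 |
| 15 / 10 / 5% | 28.3 / 21.0 / 50.7% | 68.2% | 76.7% | 8.5 |

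Worked row, 15 / 10 / 5%: contacts 2,000, 1,400 and 3,200; non-respondents 1,700, 1,260 and 3,040, total 6,000; men (1,020 + 693 + 2,888) / 6,000 = 76.7%. The within-stratum difference is zero in every row.

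A starker case leaves out rheumatologists: GPs 50% men at 15% yield, orthopaedists 90% men at 5%. Respondents: (150 + 144) / 460 = 63.9% men. Non-respondents: (850 + 2,736) / 4,740 = 75.7%. The gap is about 12 points. At yields of 12% and 8% it is about 4: (1,100 + 1,656) / 4,040 = 68.2%.

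**Step 3: pooling can hide real bias.** Assume 3,000 GPs and 3,000 specialists are contacted, half of each older, with 300 respondents from each. Let 60% of GP respondents and 40% of specialist respondents be older. Non-respondents are then (1,500 − 180) / 2,700 = 48.9% and (1,500 − 120) / 2,700 = 51.1% older. Pooled, it is 300/600 = 50.0% against 2,700/5,400 = 50.0%. Two opposite biases of 11 points vanish, here even at equal yields.

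**Step 4: who is a respondent.** Take one stratum, half the list older, everyone equally willing to answer.

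- *Analysable prescribers only.* With assumed prescriber shares of 60% (older) and 40% (younger), respondents are 0.30 / (0.30 + 0.20) = 60.0% older against 50.0% of non-respondents. With 80% and 40%, it is 0.40 / (0.40 + 0.20) = 66.7% against 50.0%. That is 10 to 17 points with no response bias.
- *Everyone who answered, screened-out non-prescribers included.* The gap is 0. The comparison then does not describe the analysed 600. Section 9.7.2 gives a cooperation rate and section 9.8.2 a percentage of non-analysable questionnaires, but neither plans to compare characteristics at that stage.

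**The case against.** The strongest defence is that the protocol never says age, gender and practice type will be pooled. Sections 4.9 and 9.7.1 present results by country and specialty as a general rule, and the region item in section 4.9 would fit a comparison made inside countries. Table layout is commonly left to a SAP, which is not at hand. This stands. A reader might infer that the check pools all strata, but for these three variables the text leaves the matter open. It does not rescue the country and specialty comparison, which is stated and can only run across strata.

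A reader might also infer that prescribers are compared with a mixed group. Sections 9.5.2 and 9.7.2 favour the wider meaning of respondent, and section 9.9.2 speaks of participants; on that reading the eligibility mismatch disappears. This also stands. What remains is the undefined term in section 9.7.1 and the uncompared loss after participation. Section 9.7.2 does say that reasons for non-response will be sought from the observed variables, which goes part of the way without fixing a comparison.

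Finally, the check is descriptive, volunteer and web-survey bias are already listed as limitations, and the inputs behind the magnitudes are assumed, the cancellation in step 3 being constructed. All true: the figures show what can happen, not what is likely.

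**Conclusion.** The point holds for the part the protocol fixes. As a measure of selection bias, comparing country and specialty is uninformative under quota recruitment: it returns yield per stratum, which the weights already correct. This needs no assumed input; it presumes only that quotas are filled, and section 9.5.2 allows for exhausted lists.

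The rest is conditional. If age, gender and practice type are compared without stratification, false imbalance of about 3 to 12 points arises at the unequal yields tried and none at equal yields, and real bias can cancel. If respondent means analysable prescribers, differences between prescribers and non-prescribers enter the comparison; if it means all participants, loss before an analysable questionnaire is counted but not characterised.

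It would be too strong to conclude that the main results are biased or the sample too small. Generalisation in section 9.9.5 rests on the weights, and neither the weighted estimates nor the 600 depend on this check. It is worth changing because a better comparison is available at little cost.

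**What to change.** Reword sections 9.7.1, 9.9.2 and 4.9 consistently.

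1. Compare all physicians who answered the screener, including those screened out as non-prescribers, with those approached who did not answer. Use the available list characteristics, within country-by-specialty stratum or standardised to a common stratum mix. This isolates response.
2. Among physicians who passed the screener, compare analysable with non-analysable questionnaires in the same way. This isolates loss among known prescribers.
3. Report country and specialty differences as yield per stratum, not as a measure of selection bias.
4. Define respondent once and use it in that sense throughout.

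The cost is wording and two sets of descriptive tables. Section 9.6.1 records contacts and completion per physician and section 10.3.2 gives each physician a unique link, so the data should be at hand. Because answers are collected anonymously, the sponsor should confirm that the screener answer can be tied to the list record. Two limits remain. Stratum quotas are 30 to 90, so standardised totals should be the main display. Section 9.5.1 warns that age and gender may be missing from the lists in some countries, so the tables should say where each characteristic is available.

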#### Handling of missing data:

The number of missing data will be indicated. Missing data will not be replaced by imputation methods. They are expected to be few and distributed at random.

### 9.7.2 Analysis of non-participation or refusal to participate rate

As often required by the Authorities, the following different cases of total non-response will be distinguished and analysed:

- Targeted physicians: Physicians reached to whom an email or mail has been sent, or have been called.

- Contacted physicians: Physicians who have been reached out by phone or have opened their email (if technically available in their country).
- Physicians who agreed to participate: Physicians willing to participate in the survey (e.g. by phone or by clicking on the link provided in the recruitment email).
- Physicians with complete questionnaire: Physicians who actually completed the questionnaire until its end.

The physicians' participation in the survey will be examined via different ratios:

- Contact rate = contacted physicians / targeted physicians
- Response rate = Physicians who agreed to participate / contacted physicians
- Cooperation rate = Physicians with complete questionnaire / Physicians who agreed to participate
- Refusal rate = (contacted physicians-physicians who agreed to participate) / Physicians reached

The reasons for non-response will be sought, especially from all observed variables. This will ensure that missing data are reported with enough details to strengthen the results validity, as recommended by the STROBE guidelines (12).

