### 9.2.2 Exclusion criteria

Inactive and retired physicians (when documented information is available to identify them) will be deleted from the contact lists before randomisation.

The following exclusion criteria will be checked at the beginning of the web questionnaire:

- Physicians who do not treat patients
- Physicians who may have conflicts of interest with the survey (i.e. physicians employed by regulatory bodies, pharmaceutical industries).

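### The cooperation rate in section 9.7.2 is not tied to eligibility, so it does not measure break-off among eligible physicians

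*Protocol*

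**What the plan says.** Section 9.7.2 of the protocol sets up four nested groups of physicians (targeted, contacted, agreed, complete) and builds its participation ratios from them. One is "Cooperation rate = Physicians with complete questionnaire / Physicians who agreed to participate". The denominator is described as "Physicians willing to participate in the survey (e.g. by phone or by clicking on the link provided in the recruitment email", and the numerator as "Physicians who actually completed the questionnaire until its end". Neither carries an eligibility condition, and there is no group for physicians found to be ineligible.

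Eligibility is settled later. Section 9.2.1 requires "Physicians who prescribed systemic thiocolchicoside within the 12 months prior to the survey". The contact lists are drawn by specialty, not by prescribing, so section 9.5.1 adds that "a screening question will check whether the physician has prescribed systemic thiocolchicoside within the last 12 months". Section 9.3 lists this as a yes/no item under the label Screener. For the other criteria (not treating patients, conflict of interest), section 9.2.2 states: "The following exclusion criteria will be checked at the beginning of the web questionnaire".

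Section 9.5.2 expects about 30% of physicians either not to finish or not to be analysable, and names "physicians without any prescription of systemic thiocolchicoside in the last 12 months" among them. The note under Table 9.5.2–3 then attributes the whole 30% to physicians who do not complete.

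**The concern.** Two different events sit between agreeing and completing. An eligible prescriber may start and break off, which can signal non-response bias. A non-prescriber may be correctly turned away, which says nothing about bias in the target population. The formula does not separate them, and the sample size section already combines them in one 30% figure.

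Section 9.7.2 offers these ratios to the authorities so that non-response is reported in enough detail to support the validity of the results. A reader who sees a cooperation rate well below 100% will want to know whether prescribers were lost. The rate as defined cannot answer that.

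**Working it through.** **Inputs.** From section 9.5.2: P = 50%, half-width 4%, 95% confidence, 600 analysable questionnaires, 780 participating physicians. The protocol states no cooperation rate, no split of the expected losses by cause, and no prescriber share among physicians who agree.

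**The plan's own figures.** n = P(1 − P)z²/e² = 0.25 × 1.96² / 0.04² = 600.2, which matches the stated 600. 600 × 1.30 = 780, which matches the stated 780.

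**What the formula measures.** Among physicians who agreed, let s be the share who are eligible, c the share of eligible physicians who finish, and d the share of ineligible physicians who reach the end.

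- Rate as defined = s × c + (1 − s) × d.
- Break-off among eligible physicians depends on c alone.
- If a negative screener ends the questionnaire, d = 0 and the rate is s × c, so ineligibility lowers it.
- If non-prescribers can continue, d is above 0 and ineligible physicians enter the numerator.
- The rate equals c only if everyone who agrees is eligible (s = 1) or the two groups happen to finish equally often (d = c).

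**Which case applies.** No sentence says that a negative answer ends the questionnaire. Stopping is implied by the inclusion criterion in 9.2.1, the label Screener in 9.3, and the placing of non-prescribers in the expected loss in 9.5.2.

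**Illustration on the planning totals.** This takes 780 as agreed, 600 as complete, and d = 0. The protocol makes neither of the first two identifications: 9.7.2 defines agreement by willingness or a click, and 600 counts analysable questionnaires.

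Rate as defined = 600/780 = 76.9%, whatever caused the 780 − 600 = 180 losses.

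Rate among eligible physicians = 600/(780 − number ineligible), over the full range of the unstated split:

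| Share of the 180 losses that is ineligible (assumed) | Number ineligible | Rate among eligible |
|---|---|---|
| 0% | 0 | 600/780 = 76.9% |
| 25% | 45 | 600/735 = 81.6% |
| 50% | 90 | 600/690 = 87.0% |
| 75% | 135 | 600/645 = 93.0% |
| 100% | 180 | 600/600 = 100% |

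The same reported 76.9% fits both heavy loss of prescribers and none at all.

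**The case against.** The strongest reply is that completers over agreers is a coherent funnel ratio, that section 9.7.2 never claims it is limited to eligible physicians, and that the counts needed for the split should exist anyway. The screener answer is a collected variable, section 9.7.2 promises to look into why physicians did not respond, and section 9.8.2 counts non-analysable questionnaires. This stands in part: the data will be there. But none of these provisions changes the formula. A physician correctly screened out is not a non-respondent, and section 9.8.2 asks for one overall percentage without a cause. Nor is this a detail left to an analysis plan, because the protocol writes the formula out.

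It can also be said that termination at the screener is inferred. Section 9.5.2 allows for a physician who finishes but is not analysable. Its prescription sample assumes that only 50% of interviewed physicians prescribed to patients, which is hard to square with certain removal at a screener. That is correct, and it is why the point is put conditionally. It changes the direction of the distortion, not the absence of an eligibility condition.

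A reader might go further and infer that the rate will show false differences between countries and specialties, since strata with fewer prescribers would appear to cooperate less. The algebra points that way when d = 0, and section 9.5.2 expects enough prescribing rheumatologists and orthopedists to be hard to recruit. But section 9.7.2 does not say that the ratios are computed by stratum, and no prescriber shares are given, so the documents support no figure for such a gap. A reader might also infer that the survey's main results are biased by this. They are not: the cooperation rate enters no weight, confidence interval or proportion of correct answers.

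**Conclusion.** The point holds as a defect in a stated definition. The cooperation rate mixes eligibility with completion and, in general, does not give break-off among eligible physicians, whether or not a negative screener ends the questionnaire. On the planning totals, a reported 76.9% is compatible with anything from 76.9% to 100% among eligible physicians. That range assumes that 780 stands for agreed, that 600 stands for complete, and that ineligible physicians do not reach the end; the split of the 180 losses is not given. The consequence is limited to the descriptive participation measure used to judge non-response. It is worth correcting because the figure would otherwise mislead and the correction is small.

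**What to change.** In section 9.7.2:

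1. Add a category for physicians screened out as ineligible, covering both the exclusion criteria and the prescriber question, and state whether a negative answer ends the questionnaire.
2. Define cooperation rate = eligible physicians with a complete questionnaire / (physicians who agreed − physicians screened out). Note that those who agreed but never answered the screener have unknown eligibility and stay in the denominator, so the rate may still understate completion among eligible physicians.
3. Report an eligibility rate = physicians passing the screener / physicians answering it, preferably by country and specialty.

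The cost is one formula, one category and one line in the participation table. The screener and exclusion answers are already collected, so no new data are needed and the sample size does not change.
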